7.5. Analysis of the Other Secondary Efficacy Parameters

All other secondary efficacy analyses will be conducted for the ITT Population in the DBVC period.

7.5.1. Continuous Efficacy Endpoints

The summary and analysis of statistics for the following continuous parameters, including change and percentage change (if applicable) from baseline, will be presented by treatment group and visit:

- By-visit WI-NRS score
- By-visit Skin Pain NRS score
- DLQI total and subscale scores
- EQ VAS score

The summary statistics include sample size, mean, median, standard deviation, minimum, maximum, first quartile, third quartile, and 95% CI. A mixed model for repeated measures with the fixed effect of the treatment group (ruxolitinib 1.5% cream and vehicle cream), randomization stratification factors, visit, and visit by treatment interaction may be fit for the comparison between ruxolitinib 1.5% cream and vehicle cream.

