10.4.3. Secondary Analyses

Secondary efficacy analyses will be conducted on the ITT population. For the time to achieve \geq 2-point or \geq 4-point improvement from baseline in WI-NRS, a log rank test stratified by randomization stratification factors will be used for between-treatment group comparisons. The hazard ratio and its 95% CI will be estimated based on the stratified Cox regression model using Efron's method accounting for ties. Kaplan-Meier curves will be presented by treatment groups. The number of participants, number of events, and number of censoring will be summarized by treatment groups. The Kaplan-Meier estimate of median time will be presented with its 95% CI. The 95% CI will be calculated using the method by Brookmeyer and Crowley (1982).

All other secondary and exploratory efficacy variables will be summarized using descriptive statistics. For categorical measurements, summary statistics will include sample size, frequency, and percentages. Similar stratified CMH test as specified in the primary and key secondary analysis will be used if applicable. For continuous measurements, summary statistics will include sample size, mean, median, standard deviation, standard error of the mean, minimum, and maximum. Continuous efficacy endpoints, including the actual measurement, change from baseline, and percentage change from baseline, may also be analyzed by the mixed model for repeated measures.

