1. INTRODUCTION

INCB 18424-319 is a Phase 3, multicenter, randomized, DBVC, parallel-group study in adults with PN (IGA-CPG-S score of ≥ 2 ; ≥ 6 pruriginous lesions on ≥ 2 different body areas; and PN-related WI-NRS score ≥ 7). Approximately 180 participants will be randomized 1:1 to 1 of 2 treatment groups (ruxolitinib 1.5% cream BID or vehicle cream BID) stratified by baseline IGA-CPG-S score (2 or ≥ 3) and geographic region (North America or outside of North America). Participants with an IGA-CPG-S score of 2 will constitute up to approximately 20% of the overall study population.

Participants will apply blinded study treatment for 12 weeks followed by a 40-week OLE period. During the OLE period, all participants, including those initially randomized to vehicle, will apply ruxolitinib 1.5% cream BID. A 30-day post-treatment, safety follow-up visit will be conducted after the OLE period.

The purpose of this SAP is to provide details of the statistical analyses that have been outlined in the study Protocol. The Department of Biostatistics or designee will execute the scope of this plan, and the Department of Clinical Pharmacokinetics or designee will execute the analyses of PK.

Another Phase 3 study, INCB 18424-320, has a study design identical to INCB 18424-319. This SAP applies to both the INCB 18424-319 and INCB 18424-320 studies.

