2.2. Study Objectives and Endpoints

Table 1 presents the objectives and endpoints.

Table 1: Objectives and Endpoints

Objectives	Endpoints
Primary	
To demonstrate the efficacy of ruxolitinib 1.5% cream BID in participants with PN.	WI-NRS4 response at Week 12, defined as achieving a ≥ 4-point improvement (reduction) in WI-NRS score from baseline.
Key Secondary	
To further demonstrate the treatment effects of ruxolitinib 1.5% cream BID in participants with PN.	 WI-NRS4 response at Week 4. Overall-TS at Week 12, defined as achieving both a WI-NRS4 response and an IGA-CPG-S-TS. (IGA-CPG-S-TS is defined as an IGA-CPG-S score of 0 or 1 with a ≥ 2 grade improvement from baseline) IGA-CPG-S-TS at Week 12. WI-NRS4 response on Day 7.
Secondary	
To further demonstrate the treatment effects of ruxolitinib 1.5% cream BID in participants with PN.	 WI-NRS4 response at each postbaseline visit. Change from baseline in WI-NRS score at each postbaseline visit. Time to ≥ 2-point improvement from baseline in WI-NRS score. Time to ≥ 4-point improvement from baseline in WI-NRS score. Achieving a ≥ 2-point improvement (reduction) in Skin Pain NRS score from baseline. Change from baseline in Skin Pain NRS score at each postbaseline visit. IGA-CPG-S-TS at each postbaseline visit. IGA-CPG-A score of 0 or 1 with a least a 2-grade improvement (reduction) at each postbaseline visit. Achieving > 75% healed lesions from PAS at each postbaseline visit.

Table 1: Objectives and Endpoints (Continued)

Objectives	Endpoints
Secondary (continued)	
To evaluate the effect of ruxolitinib 1.5% cream BID on QOL.	 Change from baseline in DLQI score at each postbaseline visit. Change from baseline in EQ-5D-5L score at each postbaseline visit.
To evaluate the safety and tolerability of ruxolitinib 1.5% cream BID in participants with PN.	The type, frequency, and severity of AEs, including changes in vital signs and clinical laboratory blood samples.
Exploratory	

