4.1.3. Baseline Value

For the DBVC period, baseline is the last nonmissing measurement obtained before or on the day of the first application of ruxolitinib 1.5% cream or vehicle cream in the DBVC period, unless otherwise defined.

For randomized participants not treated with any study cream, baseline is defined as the last nonmissing assessment before or on the date of randomization.

For participants who continue in the OLE period, baseline is defined as follows:

- For efficacy evaluations in the OLE period, baseline is the last nonmissing measurement obtained before or on the day of the first application of study treatment in the DBVC period.
- For safety evaluations in the OLE period, baseline is the last nonmissing measurement obtained before or on the day of the first application of ruxolitinib 1.5% cream in the study.

When a scheduled assessment and an unscheduled assessment occur on the same day and the times of the assessments are not available, use the following convention to determine baseline:

- If both a scheduled and an unscheduled visit are available on the day of the first application and the time is missing, use the scheduled assessment as baseline.
- If the scheduled assessment is missing on the day of the first application and an unscheduled assessment is available, use the unscheduled assessment as baseline.

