7.2. Efficacy Measures

7.2.1. Worst-Itch Numeric Rating Scale

The WI-NRS is a PRO comprised of a single item rated on a scale from 0 ("No itch") to 10 ("Worst imaginable itch"). Each evening beginning on the day of screening through Week 52 or ET, the participant will assess their worst level of PN-related itch during the past 24 hours on a scale of 0 to 10 in an eDiary.

The WI-NRS score for baseline will be determined by averaging the 7 daily WI-NRS scores before Day 1 (ie, Days -7 to -1) for all by-visit summaries. The by-visit WI-NRS score for postbaseline visits will be determined by averaging the 7 daily WI-NRS scores before the visit day. If 4 or more daily scores are missing (out of the 7), the WI-NRS score at the visit will be set to missing. For all daily WI-NRS-related analyses, baseline will be defined as the last available daily WI-NRS score during the last week prior to Day 1 (ie, Days -7 to -1).

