7.2.5.1. Skin Pain Numeric Rating Scale

Participants will be instructed to complete and record the Skin Pain NRS in a diary each evening, beginning on the day of screening through Week 52 or treatment discontinuation, whichever comes first. The participants will assess their worst level of PN-related skin pain during the past 24 hours on a scale of 0 to 10.

The Skin Pain NRS score for baseline will be determined by averaging the 7 daily NRS scores before Day 1 (ie, Days –7 to –1) for all by-visit summaries. The by-visit Skin Pain NRS score for postbaseline visits will be determined by averaging the 7 daily NRS scores before the visit day. If 4 or more daily scores are missing (out of the 7), the Skin Pain NRS score at the visit will be set to missing. For all daily pain-related analyses, baseline will be defined as the last available daily pain NRS score during the last week prior to Day 1 (ie, Days –7 to –1).

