10. PLANNED ANALYSES

No formal interim analysis is planned in this study.

There are 2 formal planned analyses as follows:

- The primary analysis will occur after the primary database lock, when all participants have completed or discontinued from the DBVC period. The sponsor will be unblinded after the primary database lock; however, investigators and participants will remain blinded to the individual study treatment assignment after the primary database lock.
- The final analysis will occur when all participants have completed or withdrawn from the study.

If the p-value for the primary endpoint is deemed insignificant in the primary analysis outlined in Section 7.3.1, the study will be terminated due to a lack of demonstrable efficacy benefits for the participants.

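### The optional mixed model for the continuous secondary endpoints omits the outcome's own baseline value, which gives up precision that is almost free to recover

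*SAP*

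**What the plan says.** SAP 7.5.1 covers four continuous outcomes: by-visit WI-NRS, by-visit Skin Pain NRS, DLQI total and subscale scores, and EQ VAS. It first names treatment group as a fixed effect of the mixed model and then lists the remaining terms: "randomization stratification factors, visit, and visit by treatment interaction may be fit for the comparison between ruxolitinib 1.5% cream and vehicle cream". No baseline value of the outcome appears, and no other visible text in the SAP adds one.

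Protocol 10.4.3 names no model terms. It says only that continuous endpoints, "including the actual measurement, change from baseline, and percentage change from baseline, may also be analyzed by the mixed model for repeated measures".

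The baseline values already exist. SAP 4.1.3 gives the general rule: "For the DBVC period, baseline is the last nonmissing measurement obtained before or on the day of the first application". The two diary scales have their own definitions, in SAP 7.2.1 ("The WI-NRS score for baseline will be determined by averaging the 7 daily WI-NRS scores before Day 1") and SAP 7.2.5.1 ("The Skin Pain NRS score for baseline will be determined by averaging the 7 daily NRS scores before Day 1").

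The related secondary endpoints in SAP 2.2 are changes from baseline, for example "Change from baseline in DLQI score at each postbaseline visit".

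**The concern.** A between-arm comparison of change from baseline is normally adjusted for the baseline value, because without it the treatment difference can carry variance that a known covariate would remove. The only baseline information in this model is the pair of stratification factors: IGA-CPG-S grade (2 or at least 3) and region. Neither measures baseline itch, pain, DLQI or EQ VAS.

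The omission looks unintended. Where the SAP sets out regression models for imputing WI-NRS (SAP 7.3.3.3 and the Day 7 analysis in SAP 7.4), baseline WI-NRS is included.

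Two things are at stake:

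- **Precision.** Confidence intervals for the continuous secondary endpoints may be wider than they need to be.
- **Choice of response.** The protocol allows the score, the change and the percentage change as responses, and SAP 7.5.1 does not say which one the model uses. Without baseline in the model, score and change give different estimates and standard errors. With baseline, they give the same treatment difference and standard error. Percentage change still differs.

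**Working it through.** **The plan's own figures.** The plan states no figure for this model. Its only power figures are for the binary endpoints (Protocol 10.1, SAP 3.3). With 90 per arm and a two-sided Fisher exact test at 0.05 they reproduce:

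- primary: 92.3% (stated above 90%)
- WI-NRS4 at Week 4: 95.9% (above 90%)
- Overall-TS and WI-NRS4 on Day 7: 90.6% each (above 90%)
- IGA-CPG-S-TS: 80.2% (80%)

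None of these depends on the mixed model.

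**Inputs.** From the documents: about 180 participants randomized 1:1, so 90 per arm, and a baseline WI-NRS of at least 7 (Protocol 5.1, criterion 6) on a 0-10 scale. The documents give no standard deviation or correlation for any of the scales, so those are assumptions.

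**Formula.** Let s1 be the follow-up SD, k the baseline SD divided by s1, and rho the baseline-to-follow-up correlation. For a change score at one visit:

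- variance without baseline: s1²(1 + k² − 2·rho·k)
- variance with baseline: s1²(1 − rho²)
- difference: s1²(k − rho)², which is never negative and is zero when rho = k
- reduction in CI width: 1 − √[(1 − rho²)/(1 + k² − 2·rho·k)]

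**WI-NRS.** Baseline lies in 7-10. If it is uniform, its SD is 3/√12 = 0.87. SD ratios of 0.5 and 0.33 then correspond to follow-up SDs of 0.87/0.5 = 1.7 and 0.87/0.33 = 2.6.

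| k | rho 0.1 | rho 0.2 | rho = k |
|---|---|---|---|
| 0.5 | 7.2% | 4.4% | 0.0% |
| 0.4 | 4.3% | 2.0% | 0.0% |
| 0.33 | 2.6% | 0.9% | 0.0% |

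Example: k = 0.5 and rho = 0.2 give 1 − √(0.96/1.05) = 4.4%. The 0-4% range takes rho from 0.2 up to k.

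**Other scales.**

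| k | rho 0.2 | rho 0.3 | rho 0.5 | rho 0.7 |
|---|---|---|---|---|
| 1.0 | 22.5% | 19.4% | 13.4% | 7.8% |
| 0.85 | 16.7% | 13.4% | 7.3% | 2.1% |
| 0.7 | 10.9% | 7.8% | 2.6% | 0.0% |

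Example: k = 1 and rho = 0.5 give 1 − √(0.75/1) = 13.4%. The 0-19% range takes rho from 0.3 to 0.7.

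**Equivalent sample size.** The number per arm without baseline that matches 90 with it is 90(1 + k² − 2·rho·k)/(1 − rho²). For k = 0.5, rho = 0.2 this is 90 × 1.05/0.96 = 98.4. For k = 1, rho = 0.5 it is 90/0.75 = 120. At rho = k it is 90.

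**Simulation check.** A single-visit model with 90 per arm, two binary strata in both models and 4,000 runs gave these cuts in mean standard error:

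- k = 1, rho 0.2/0.3/0.5/0.7: 22.4/19.1/13.1/7.5%
- rho = 0.2, k 0.5/0.4/0.33: 4.1/1.7/0.6%
- zero-gain points (k = rho): the standard error was about 0.3% larger, the cost of the extra parameter

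In every run the baseline-adjusted treatment estimate was identical for raw score and change score. This follows algebraically: subtracting baseline from the response shifts only the baseline coefficient.

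**The case against.** The strongest case against raising this is that nothing in the plan is wrong. Both documents make the model optional. It carries no alpha and no stated power, and it supports endpoints that are summarized descriptively in any case. With complete data, randomization keeps the comparison unbiased without baseline. All of that stands, and it is why the point ranks low. It does not justify leaving the term out: if the model is run, baseline improves it at negligible cost, and if it is not run, the change costs nothing.

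A second objection is that the percentage ranges depend on chosen inputs. That also stands. Other values, which the documents do not exclude, give more: for WI-NRS at k = 0.33, rho of 0.6 gives 5.3% and 0.7 gives 11.2%. On the other scales, a baseline SD larger than the follow-up SD (k = 1.25) gives 20-32% for rho from 0.2 to 0.8. The tabulated ranges are illustrations, and these alternatives show a larger gain. At the other end, the net effect can be a loss of about 0.3%.

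Third, the arithmetic assumes the change score as response. If the raw score were modelled, the gain would be 1 − √(1 − rho²): 4.6% at rho 0.3 and 13.4% at 0.5.

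Finally, SAP 7.5.1 does not name the response, covariance structure or degrees-of-freedom method, and the single-visit simulation cannot assess a baseline-by-visit term. Both remarks are correct. Neither weakens the case for including baseline, and once it is included the choice between score and change no longer affects the treatment difference.

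**Conclusion.** The concern holds. The specified model leaves out the outcome's baseline value, and no visible text supplies it. The cost is mainly precision. Under the stated assumptions the change-score CI is 0-4% wider than it need be for WI-NRS, expressed as the narrowing that baseline would bring, and 0-19% for Skin Pain NRS, DLQI and EQ VAS. These figures rest on assumed SD ratios and correlations, on a single visit, and on no allowance for variance already absorbed by the stratification factors. No bias is claimed. The primary analysis, the key secondary tests, the fixed sequence and the sample size are untouched. The omission itself is certain; its size cannot be determined from the documents.

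**What to change.** In SAP 7.5.1, add the baseline value of the outcome and its interaction with visit to the fixed effects of the mixed model.

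The timing matters because "This SAP applies to both the INCB 18424-319 and INCB 18424-320 studies" and "The sponsor will be unblinded after the primary database lock". The amended version should therefore be dated before the first unblinding of either study.

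The cost is one SAP amendment (the current version is the original, dated 15 JUL 2024) with one added phrase and no new data. Protocol 10.4.3 lists no model terms, so nothing there conflicts. Statistically the change uses a few degrees of freedom. If the raw score is the response, participants without a scored baseline, such as a DLQI with two or more unanswered questions (SAP 7.2.5.2), would drop out of the model. Change scores already need a baseline, so for them nothing is lost.

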7.5.2. Categorical Efficacy Endpoints

For the following categorical parameters, summary statistics, including sample size, frequency, and percentages will be presented by treatment group and visit.

- WI-NRS4 response
- \geq 2-point improvement in Skin Pain NRS score from baseline
- IGA-CPG-S-TS
- IGA-CPG-A-TS
- > 75% healed lesions from PAS
- Each category of each EQ-5D-5L dimension

For the endpoint \geq 2-point improvement in Skin Pain NRS score from baseline, the analysis will be conducted on the ITT Population in the DBVC period with a baseline Skin Pain NRS score of \geq 2. The analysis for IGA-CPG-A-TS will be conducted on the ITT Population in the DBVC period with baseline IGA-CPG-A score of \geq 2.

For the endpoints with binary outcomes based on WI-NRS, Skin Pain NRS, IGA-CPG-S, IGA-CPG-A, and PAS scores, missing postbaseline values will be imputed as nonresponders. A similar CMH test as specified for the primary endpoint may be fit for the binary endpoints at Week 12 visit.

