2.2.1. Scientific Rationale for Study Design

This Phase 3 study will investigate the efficacy and safety of ruxolitinib 1.5% cream BID versus vehicle cream BID in participants with PN (IGA-CPG-S score of $\geq 2, \geq 6$ pruriginous lesions on ≥ 2 different body areas, and PN-related WI-NRS score ≥ 7). The total estimated BSA treatment area must be $\leq 20\%$. This design will provide a well-controlled assessment of the efficacy of ruxolitinib 1.5% cream in participants with PN while minimizing the treatment duration for participants assigned to vehicle cream. Further, the 40-week OLE period will provide the participants who are initially randomized to vehicle cream the opportunity to receive ruxolitinib 1.5% cream, and it is an adequate duration to assess the safety and efficacy of intermittent dosing with ruxolitinib 1.5% cream.

Based on 2 Phase 3 pivotal studies (INCB 18424-303 and -304) in participants \geq 12 years of age with mild to moderate AD affecting 1% to 20% BSA (excluding the scalp), ruxolitinib 1.5% cream BID was statistically significantly superior to vehicle cream after 8 weeks of treatment for the primary endpoint, IGA-TS (IGA score of 0 or 1 with \geq 2-grade improvement from baseline). Furthermore, statistically significant improvement was observed on the key secondary endpoints, including EASI75 and \geq 4-point improvement in Itch NRS score (Papp et al 2021).

In PN, disease healing is characterized by flattening of the lesions, with the base of the lesions remaining unchanged. A white or colored scar may remain after lesion clearance. In a static assessment of lesions, the stage of elevation or flattening for multiple lesions cannot be compared with previous visits.

Zeidler (2021) reported that for chronic prurigo, the number of lesions is representative of the stage of the disease. The presence of excoriation to the lesion(s) reflect(s) scratching activity, which is an early sign of CPG improvement (ie, the resolution of crusts and erosions from the top of the lesions). Two IGAs were validated to assess the stage (number of lesions) and the scratching activity of chronic prurigo, IGA-CPG stage, and IGA-CPG activity.

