3. OBJECTIVES AND ENDPOINTS

Table 5 presents the objectives and endpoints.

Table 5: Objectives and Endpoints

Objectives	Endpoints					
Primary						
To demonstrate the efficacy of ruxolitinib 1.5% cream BID in participants with PN.	WI-NRS4 response at Week 12, defined as achieving a ≥ 4-point improvement (reduction) in WI-NRS score from baseline.					
Key Secondary						
To further demonstrate the treatment effects of	WI-NRS4 response at Week 4.					
ruxolitinib 1.5% cream BID in participants with PN.	Overall-TS at Week 12, defined as achieving both a WI-NRS4 response and an IGA-CPG-S-TS.					
	(IGA-CPG-S-TS is defined as an IGA-CPG-S score of 0 or 1 with $a \ge 2$ grade improvement from baseline)					
	• IGA-CPG-S-TS at Week 12.					
	• WI-NRS4 response on Day 7.					
Secondary						
To further demonstrate the treatment effects of	WI-NRS4 response at each postbaseline visit.					
ruxolitinib 1.5% cream BID in participants with PN.	Change from baseline in WI-NRS score at each postbaseline visit.					
	• Time to ≥ 2-point improvement from baseline in WI-NRS score.					
	• Time to ≥ 4-point improvement from baseline in WI-NRS score.					
	• Achieving a ≥ 2-point improvement (reduction) in Skin Pain NRS score from baseline.					
	Change from baseline in Skin Pain NRS score at each postbaseline visit.					
	IGA-CPG-S-TS at each postbaseline visit.					
	• IGA-CPG-A score of 0 or 1 with at least a 2 grade improvement (reduction) at each postbaseline visit.					
	Achieving > 75% healed lesions from PAS at each postbaseline visit.					

Table 5: Objectives and Endpoints (Continued)

Objectives	Endpoints
To evaluate the effect of ruxolitinib 1.5% cream BID on QOL.	 Change from baseline in DLQI score at each postbaseline visit. Change from baseline in EQ-5D-5L score at each postbaseline visit.
To evaluate the safety and tolerability of ruxolitinib 1.5% cream BID in participants with PN.	The type, frequency, and severity of AEs, including changes in vital signs and clinical laboratory blood samples.
Exploratory	

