8.2.3. Prurigo Activity Score

The extent and severity of PN will also be assessed via the PAS (v1.2) and will be determined at the visits noted in the SoA (see Table 3 and Table 4). The first 3 items are descriptive of the type, predominant type, distribution, and quantity of pruriginous lesions. The remaining 2 items of the PAS will assess disease activity in terms of percentage (ie, 0%, 1%-25%, 26%-50%, 51%-75%, 76%-100%) of pruriginous lesions with excoriations/crusts on top (to reflect active scratching), and the percentage (100%, 76%-99%, 51%-75%, 26%-50%, 0%-25%) of healed pruriginous lesions, in order to quantify change of PN skin lesions. In addition, the total number of pruriginous lesions in a representative area will be identified at screening and followed throughout the study.

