7.2.3. Prurigo Activity Score

The extent and severity of PN will also be assessed via the PAS (v1.2). The first 3 items are descriptive of the type, predominant type, distribution, and quantity of pruriginous lesions. The remaining 2 items of the PAS will assess disease activity in terms of percentage (ie, 0%, 1%-25%, 26%-50%, 51%-75%, and 76%-100%) of pruriginous lesions with excoriations/crusts on top (to reflect active scratching) and the percentage (ie, 100%, 76%-99%, 51%-75%, 26%-50%, and 0%-25%) of healed pruriginous lesions in order to quantify change of PN skin lesions. In addition, the total number of pruriginous lesions in a representative area will be identified at screening and followed throughout the study.

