2.1.3.2	Summary and Analysis of By-Visit WI-NRS Score in the OLE Period	OLE Safety	
2.1.4	Summary and Analysis of Time to ≥ 2-Point Improvement in Daily WI-NRS Score From Baseline During the DBVC Period	ITT (baseline daily WI-NRS score ≥ 2)	
2.1.5	Summary and Analysis of Time to ≥ 4-Point Improvement in Daily WI-NRS Score From Baseline During the DBVC Period	ITT (baseline daily WI-NRS score ≥ 4)	
2.1.3	Summary and Analysis of Daily WI-NRS Score From Baseline to Day 14	ITT	
2.2.1	Summary and Analysis of Participants Achieving Overall-TS in the DBVC Period	ITT	
2.2.2	Summary and Analysis of Participants Achieving Overall-TS From Day 1 to Week 52	ITT	
2.3.1	Summary and Analysis of Participants Achieving IGA-CPG-S-TS in the DBVC Period	ITT	
2.3.2	Summary and Analysis of Participants Achieving IGA-CPG-S-TS From Day to Week 52	ITT	
2.4.1	Summary and Analysis of Participants Achieving IGA-CPG-A-TS in the DBVC Period	ITT	
2.4.2	Summary and Analysis of Participants Achieving IGA-CPG-A-TS From Day 1 to Week 52	ITT	
2.5.1	Summary and Analysis of By-Visit Skin Pain NRS Score in the DBVC Period	ITT	
2.5.2	Summary and Analysis of By-Visit Skin Pain NRS Score in the OLE Period	OLE Safety	
2.5.3	Summary and Analysis of Participants Achieving ≥ 2-Point Improvement in By-Visit Skin Pain NRS Score From Baseline During the DBVC Period	ITT (baseline Skin Pain NRS score ≥ 2)	
2.5.4	Summary and Analysis of Participants Achieving ≥ 2-Point Improvement in By-Visit Skin Pain NRS Score From Baseline During the OLE Period	OLE Safety (baseline Skin Pain NRS score ≥ 2)	
2.6.1	Summary and Analysis of Participants Achieving > 75% Healed Lesions From PAS in the DBVC Period	ITT	
2.6.2	Summary and Analysis of Participants Achieving > 75% Healed Lesions From PAS in the OLE Period	OLE Safety	
2.7.1.1	Summary and Analysis of DLQI Total and Subscale Scores in the DBVC Period	ITT	
2.7.1.2	Summary and Analysis of DLQI Total and Subscale Scores in the OLE Period	OLE Safety	
2.7.2	Summary and Analysis of Participants Achieving ≥ 4-Point Improvement in DLQI Total Score in the DBVC Period	ITT (baseline DLQI total score ≥ 4)	
2.8.1.1	Summary and Analysis of EQ VAS Score in the DBVC Period	ITT	
2.8.1.2	Summary and Analysis of EQ VAS Score in the OLE Period	OLE Safety	
2.8.2.1	Summary of Participants in Each Category of Each Dimension of the EQ-5D-5L in the DBVC Period	ITT	

Table No.	Title	Population	Standard

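### The PAS healed-lesion endpoint is a postbaseline status with no baseline condition, so it mixes new healing with healing already present at entry

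*SAP*

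**What the plan says.** Protocol Section 3 (Table 5) and SAP Table 1 name the secondary endpoint as "Achieving > 75% healed lesions from PAS at each postbaseline visit". SAP 7.5.2 repeats it as "> 75% healed lesions from PAS" and adds no baseline condition. In SAP Appendix A, Table 2.6.1 is titled "Summary and Analysis of Participants Achieving > 75% Healed Lesions From PAS in the DBVC Period" and its population is plain ITT. Table 2.6.2 does the same for the OLE period on the OLE Safety Population.

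SAP 7.2.3 describes the item as the percentage "of healed pruriginous lesions in order to quantify change of PN skin lesions", recorded in five categories, of which the top two are 76%-99% and 100%.

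The four other binary responses in SAP 7.5.2 are WI-NRS4, Skin Pain NRS improvement of at least 2 points, IGA-CPG-S-TS and IGA-CPG-A-TS. Each is defined by improvement from baseline. Two also have a restricted denominator. For Skin Pain, "the analysis will be conducted on the ITT Population in the DBVC period with a baseline Skin Pain NRS score of" at least 2; and "The analysis for IGA-CPG-A-TS will be conducted on the ITT Population in the DBVC period with baseline IGA-CPG-A score of" at least 2.

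On timing, Protocol 8.2.3 says the PAS "will be determined at the visits noted in the SoA", and Protocol Table 3 marks it at screening and at Baseline/Day 1.

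On entry, Protocol 5.1 requires at least 6 pruriginous lesions, IGA-CPG-S of at least 2 and baseline WI-NRS of at least 7. None of these limits the healed percentage. Protocol 2.2.1 describes healing as flattening and adds: "A white or colored scar may remain after lesion clearance".

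**The concern.** A status endpoint measures a treatment effect cleanly only if nobody has the status before treatment. Here the entry criteria set minimums for active disease and no maximum for healed disease. Diagnosis must be at least 3 months old, with no upper limit, and healed lesions may leave visible traces. A participant with 8 active and 40 healed lesions could be eligible and would be 40/48 = 83% healed on Day 1, if old healed lesions enter the PAS denominator. If that participant stays there, every attended visit counts as a response with no improvement.

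The endpoint then mixes two things: new healing on treatment and maintenance of earlier healing. What is at stake is the interpretation and sensitivity of the only listed endpoint on the percentage of lesions healed. The planned output may not reveal the mixture. The baseline disease characteristics named in SAP 6.1.2 include IGA-CPG-S and IGA-CPG-A but not PAS, although that list is open-ended.

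**Working it through.** **Benchmark.** The plan states no power for PAS. The method was therefore checked against the plan's own figures (SAP 3.3 and Table 2; Protocol 10.1 and Table 12): two-sided Fisher exact test, alpha 0.05, 90 per arm, exact enumeration.

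| Endpoint | Rates | Stated power | Recomputed |
|---|---|---|---|
| WI-NRS4 Week 12 | 50% vs 25% | > 90% | 0.923 |
| WI-NRS4 Week 4 | 40% vs 15% | > 90% | 0.959 |
| Overall-TS Week 12 | 30% vs 10% | > 90% | 0.906 |
| IGA-CPG-S-TS Week 12 | 40% vs 20% | 80% | 0.802 |
| WI-NRS4 Day 7 | 30% vs 10% | > 90% | 0.906 |

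All agree with the plan.

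**Inputs for PAS.** From the documents: 180 participants randomized 1:1, so 90 per arm. Assumed, because the documents do not give them:
- f, the share above 75% healed at baseline: 1% to 20%.
- p1 and p2, the response rates (active, vehicle) among everyone else: 40% vs 20%, borrowed from the IGA-CPG-S-TS row, with 30% vs 10% as a second case.
- s1 and s2, the proportions of the already-healed group still above 75% at Week 12.

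**Formulas.** Observed rate in an arm = (1 − f)p + f·s. The difference is therefore (1 − f)(p1 − p2) + f(s1 − s2). If s1 = s2, the second term vanishes and the difference shrinks by (1 − f). The restricted analysis keeps p1 and p2 with about 90(1 − f) per arm.

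**Results with s1 = s2 = 1, rates 40% vs 20%.**

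| f | Observed rates | Difference (points) | Power, unrestricted | n per arm restricted | Power, restricted |
|---|---|---|---|---|---|
| 0 | 40.0% vs 20.0% | 20.0 | 0.802 | 90 | 0.802 |
| 1% | 40.6% vs 20.8% | 19.8 | 0.787 | 89 | 0.796 |
| 5% | 43.0% vs 24.0% | 19.0 | 0.729 | 86 | 0.782 |
| 10% | 46.0% vs 28.0% | 18.0 | 0.664 | 81 | 0.753 |
| 20% | 52.0% vs 36.0% | 16.0 | 0.518 | 72 | 0.697 |

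For example, at f = 10%: 0.9 × 0.40 + 0.1 = 0.46 and 0.9 × 0.20 + 0.1 = 0.28. With 30% vs 10% among the rest, unrestricted against restricted power is 0.889 vs 0.902, 0.817 vs 0.889, 0.726 vs 0.866 and 0.559 vs 0.826 at the same four values of f.

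**Unequal retention, f = 10%, 20-point difference among the rest.** Retention of 100%/100% (active/vehicle) gives 0.9 × 20 = 18 points. Retention of 100%/80% gives 18 + 0.1 × 20 = 20 points. Retention of 100%/60% gives 18 + 0.1 × 40 = 22 points.

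**How plausible is a large f?** Assume healed lesions are not counted as palpable. With 6 palpable lesions, exceeding 75% needs at least 19 healed ones (18/24 = 75.0%, 19/25 = 76.0%). With 20 palpable lesions it needs at least 61 (60/80 = 75.0%, 61/81 = 75.3%). Protocol 6.3 caps IGA-CPG-S of 2 (about 6-19 lesions) at roughly 20% of participants, so about 80% or more start with around 20 or more palpable lesions.

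**The case against.** A reader might infer that the SAP contradicts itself, protecting Skin Pain and IGA-CPG-A against this problem but not PAS. The documents do not support that. Someone with a baseline below 2 cannot fall by 2 points or 2 grades, so those cut-offs remove participants who cannot respond. The PAS issue concerns participants who already meet the target. The restrictions show only that baseline-restricted denominators are already in use.

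A reader might also infer that such participants will certainly enrol and that the difference must be diluted. Neither is established. No baseline distribution of PAS categories is given, and the lesion counts above make a large share unlikely. The PAS v1.2 form is not in the documents, so it is unknown whether old scars enter its denominator; the protocol summary's definition of pruriginous lesions names five lesion types, and flat scars are not among them. Anyone who falls to 75% or below, or has a missing visit, is a nonresponder, and worse retention on vehicle can leave the difference unchanged or larger.

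Finally, PAS is outside the fixed sequence in SAP 3.2, its Week 12 CMH test is optional, and lesion clearance is also captured by the alpha-controlled IGA-CPG-S-TS, which requires a 2-grade improvement. All of this stands and limits the weight of the point. It does not change the fact that a participant can meet the PAS criterion without improving. If retention differs by arm, the endpoint still combines maintenance with new healing.

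**Conclusion.** The point holds in a limited form. PAS response is a postbaseline status, analysed without a baseline condition, for an item that SAP 7.2.3 says is meant to quantify change, and nothing in the entry criteria prevents a participant from meeting it on Day 1. Its size depends on an unknown share. At 1% the effect is negligible: 0.2 points of difference and about 0.01 of power. At 10%, with equal retention, it is 2 points and about 0.09 of power (0.753 − 0.664). The 20% case is an upper illustration and probably too high. These figures rest on borrowed response rates and, for the direction of the effect, on similar retention in both arms. Randomization keeps the comparison valid under the null, so the issue is sensitivity and interpretation, not false-positive risk. The change is worth making because it alters nothing if no such participants enrol and gives a cleaner estimate of new healing if they do.

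**What to change.** Before unblinding, state in SAP 7.5.2 and in the population column of Tables 2.6.1 and 2.6.2 that more than 75% healed lesions is analysed among participants whose baseline PAS healed category is 75% or lower. Keep the result on the full population (ITT for 2.6.1, OLE Safety for 2.6.2) alongside it. Add baseline PAS healed category by arm to the baseline disease characteristics, and report the number excluded per arm. SAP 4.1.3 already defines the baseline value, for OLE efficacy as well.

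The cost is one SAP sentence, a table footnote and one baseline row, all from data already scheduled for collection. The downside is a slightly smaller denominator in the restricted analysis. Specifying it before unblinding avoids a post hoc choice of denominator.
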